8.3.1. Inclusion Criteria

A patient must meet all of the following inclusion criteria to be eligible for enrollment in this study:

- 1. Has provided written informed consent.
- 2. Has histologically confirmed non-resectable, metastatic gastric adenocarcinoma including adenocarcinoma of the gastroesophageal (GE) junction as defined by the American Joint Committee on Cancer (AJCC) staging classification (7th ed., 2010). Documentation of histology of the tumor (primary or metastasis) will be required prior to enrollment. Gastroesophageal junction involvement must be documented by endoscopic, radiologic, surgical or pathology report.
- 3. Has previously received at least 2 prior regimens (at least 1 cycle per regimen) for advanced disease and were refractory to or unable to tolerate their last prior therapy:
 - a. Prior regimen(s) must have included a fluoropyrimidine, platinum, and either a taxane- and/or irinotecan-containing regimen; patients whose tumors are HER2-neupositive (HER2+) must have received prior anti-HER2+ therapy if available.
 - b. Patients have progressed based on imaging during or within 3 months of the last administration of their last prior regimen.
 - c. Patients who have withdrawn from their last prior regimen due to unacceptable toxicity warranting discontinuation of treatment and precluding retreatment with the same agent prior to progression of disease will also be eligible to enter the study.
 - d. Patients who have received postoperative adjuvant chemotherapy or chemoradiotherapy, and had recurrence during or within 6 months of completion of the adjuvant chemotherapy are allowed to count the adjuvant therapy as one prior regimen for advanced disease. Patients who have received pre- and post-operative adjuvant chemotherapy, and had recurrence during or within 6 months of completion of the adjuvant chemotherapy are allowed to count the adjuvant therapy as one prior regimen only if the same regimen was administered both pre- and post-operatively.
- 4. Has measureable or nonmeasurable disease as defined by RECIST 1.1 criteria.
- 5. Is able to take medications orally (ie, study drug must not be administered via a feeding tube).
- 6. Is ≥ 18 years of age (≥ 20 years for patients in Japan).

- 7. Has an ECOG performance status of 0 or 1 CCI at time of randomization.
- 8. Has adequate organ function as defined by the following criteria:

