9.2. Protocol Deviations

A set of “protocol deviations”/“major protocol deviations” is defined as a means to measure adherence to key aspects of the protocol. Summary of all major Protocol Deviations (at study entrance and during the study period) by type of deviation will be provided.

A summary of all protocol deviations (at study entrance and during the study period) by type of deviation will be provided.

A patient will be considered as having a protocol CSR reportable deviation if she/he meets at least one of the criteria presented below. These subjects will be identified based on reviews of the data prior to final unblinding of the treatment codes.

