9.2.2. Major CSR Reportable Protocol Deviation

In addition, among all CSR Reportable Protocol Deviations, a set of “major protocol deviations” is defined as a means to measure adherence to key aspects of the protocol using pre-specified CCI analyses.

Study Entrance:

MRD1 - No histological confirmation of gastric adenocarcinoma including adenocarcinoma of the gastroesophageal (GE) junction

MRD2 - No metastatic disease

MRD3 - No measurable or nonmeasurable disease as defined by RECIST 1.1 criteria

MRD4 - Received fewer than 2 prior regimens (at least 1 cycle per regimen) of standard chemotherapy for advanced gastric or GE junction cancer or was not refractory to or was able to tolerate their last prior therapy. The regimens are supposed to meet the following criteria:

- a. Prior regimens must have included a fluoropyrimidine, platinum, and either a taxane-and/or irinotecan-containing regimen; patients whose tumors are HER2-neu-positive (HER2+) must have received prior anti-HER2+ therapy if available.
- b. Patients must have progressed based on imaging during or within 3 months of the last administration of their last prior regimen.
- c. Patients who have withdrawn from standard treatment due to unacceptable toxicity warranting discontinuation of treatment and precluding retreatment with the same agent prior to progression of disease will also be eligible to enter the study.
- d. Patients who have received postoperative adjuvant chemotherapy and radiotherapy, and had recurrence during or within 6 months of completion of the adjuvant chemotherapy are allowed to count the adjuvant therapy as one prior regimen for advanced disease. Patients who have received pre- and post-operative adjuvant chemotherapy, and had recurrence during or within 6 months of completion of the adjuvant chemotherapy are allowed to count the adjuvant therapy as one prior regimen only if the same regimen was administered both pre- and post-operatively.

MRD5 - Prior anticancer therapy within 3 weeks prior to study drug administration

MRD6 - Subject has previously received TAS-102

Study period:

MRD7 - Patient received incorrect treatment (i.e. randomized to one arm but received the other arm)

MRD8 - Other concurrent chemotherapy or radiotherapy administered while receiving study medication

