The number of patients with CSR Reportable deviations of one or more criteria and the number of patients with major CSR reportable protocol deviations will be listed and tabulated for all patients (including screen failures) and ITT population.

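### SAP 9.2.2 MRD4 joins the negated parts of inclusion 3 with 'or' where 'and' is needed, so as written it catches patients who qualified by progression alone or by intolerance alone

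*SAP*

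**What the plan says.** Protocol 8.3.1, inclusion 3, requires at least two prior regimens "for advanced disease and were refractory to or unable to tolerate their last prior therapy". Its sub-items describe the two routes. Item 3b is the progression route: "Patients have progressed based on imaging during or within 3 months of the last administration of their last prior regimen". Item 3c is the toxicity route. It covers patients withdrawn from the last regimen for unacceptable toxicity and states that those withdrawn "prior to progression of disease will also be eligible to enter the study".

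SAP 9.2.2 defines MRD4 as having had fewer than two prior regimens, "or was not refractory to or was able to tolerate their last prior therapy". Below that lead sentence it repeats the sub-criteria as items a to d. Item b restates imaging progression. Item c keeps the toxicity route open: "Patients who have withdrawn from standard treatment due to unacceptable toxicity warranting discontinuation of treatment" leads into the same statement that such patients are eligible.

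On use, SAP 9.2 says: "A patient will be considered as having a protocol CSR reportable deviation if she/he meets at least one of the criteria presented below". SAP 9.2.2 takes the major deviations from among the CSR reportable ones, and the entry-related reportable category in SAP 9.2.1 is RD1, a subject who did not meet entry criteria. SAP 9.2.2 ends by stating that "the number of patients with major CSR reportable protocol deviations will be listed and tabulated", both for all patients including screen failures and for the ITT population. It also links the major set to pre-specified analyses whose description is redacted.

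**The concern.** A deviation rule for an entry criterion should be true exactly when the criterion fails. Inclusion 3 fails on this point only when a patient was neither refractory nor intolerant. MRD4 is satisfied when either half is missing.

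Consider a patient who progressed on imaging during a last regimen that was well tolerated. That patient meets 3b, yet was able to tolerate the therapy and so falls under MRD4. A patient withdrawn for toxicity before progression meets 3c, yet was not refractory and also falls under MRD4.

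The SAP presents the major deviations as a measure of adherence to key aspects of the protocol. A rule that counts eligible patients as deviating gives a wrong count if followed exactly. It would also disagree with SAP 9.4, which separately summarises by arm the randomized patients who did not meet the inclusion or exclusion criteria.

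**Working it through.** The plan gives no figure for MRD4, so there is none to reproduce. The check is one of logic.

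**Inputs**

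- R: refractory to the last prior therapy, read as inclusion 3b (Protocol 8.3.1).
- I: unable to tolerate the last prior therapy, read as inclusion 3c (Protocol 8.3.1).
- At least two prior regimens is taken as met throughout, so that only the disputed clause is tested.

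**Rules**

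- Eligible on this point: R or I.
- Correct deviation: NOT(R or I) = (NOT R) and (NOT I), by De Morgan's law.
- MRD4 lead sentence: (NOT R) or (NOT I).

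**Truth table**

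| R | I | Eligible | Correct rule flags | MRD4 as written flags |
|---|---|---|---|---|
| yes | yes | yes | no | no |
| yes | no | yes | no | **yes** |
| no | yes | yes | no | **yes** |
| no | no | no | yes | yes |

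The two rules differ in rows 2 and 3, which are the two single-route entries. MRD4 therefore misclassifies 2 of the 3 eligible combinations. The only eligible patient it leaves alone is one who was both refractory and intolerant.

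**Do items a to d of MRD4 repair this?**

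- Row 3 (intolerance alone): item c says these patients are eligible, so MRD4 contradicts itself.
- Row 2 (progression alone): item b restates the progression requirement, but no item from a to d exempts a progressed patient from the part of the clause about having tolerated the therapy. The lead sentence stands uncorrected for this route.

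**Size**

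Let b be the share of eligible patients who were both refractory and intolerant. The literal clause flags the share 1 − b of eligible patients. The documents give no value or range for b, so the formula cannot be turned into a count.

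**The case against.** The strongest reply is that nobody would apply the sentence literally, and the SAP gives several reasons to expect that.

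- **Nesting under RD1.** Major deviations are drawn from the CSR reportable ones, and RD1 is limited to subjects who did not meet entry criteria. A patient who met 3b or 3c has no RD1 deviation to upgrade. This weakens any claim that such patients will be counted. It does not make the clause right: MRD4 as worded is then inconsistent with its parent category. The any-one-criterion sentence in SAP 9.2 can also be read as making MRD4 sufficient by itself.
- **Visible intent.** Items b and c repeat the protocol routes. This stands for the toxicity route, where item c is explicit. For the progression route the intent has to be inferred.
- **Drafting style.** MRD3 also puts an 'or' under a negation and plainly means 'neither'. But MRD3 has one negation covering both terms. MRD4 negates each half separately and then joins them with 'or', so its grammar does not yield 'neither'.
- **Identification by review.** SAP 9.2 has these subjects identified by data review before final unblinding, and SAP 9.2.1 refers to a Protocol Deviation Plan that is not among the documents. Coding may well follow the intended meaning. That stands, and it is why the point concerns what the rule says and not what was recorded.

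A reader might infer two stronger things. The first is that most of the roughly 500 patients would be reported as ineligible. That needs an assumed split between routes, which nothing in the documents supports, and mechanical use of one clause in isolation. The second is that efficacy analyses would be run on the wrong patients. The visible SAP does not show this: the ITT, AT and TR populations in section 7 are defined without reference to major deviations, and section 7 defines no per-protocol set. What the redacted analyses do with the flag is unknown.

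**Conclusion.** The lead sentence of MRD4 is an incorrect negation of inclusion 3. If applied as written, it would make major deviators of patients who entered validly by progression alone or by intolerance alone. That contradicts Protocol 8.3.1, MRD4's item c and RD1.

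The consequence is limited. The visible effect is on the major-deviation listings and tables, including those for the ITT population. Any redacted pre-specified analysis that uses the flag would also be exposed. Primary overall survival is compared in all randomized patients (SAP 7.1 and 10.4.1) and does not depend on the flag. The number of patients affected cannot be derived.

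The conclusion assumes that 3b and 3c are what inclusion 3 means by refractory and intolerant, which is the natural reading of the protocol. It does not assume that anyone was actually misclassified. The point is worth correcting because this is a pre-specified rule that must be disregarded to give a sensible answer, and the correction is small.

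**What to change.** In SAP 9.2.2, replace only the faulty clause of the MRD4 lead sentence with: *or was neither refractory to nor unable to tolerate their last prior therapy (meets neither inclusion 3b nor 3c)*. Leave the rest of the lead sentence unchanged, including its reference to standard chemotherapy for advanced gastric or GE junction cancer; any change there is a separate question.

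Identify the deviation from the recorded status on 3b and 3c, before unblinding, and check that the Protocol Deviation Plan uses the same rule. Under the corrected clause only the last row of the truth table is flagged.

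The cost is one clause of SAP text and a matching check in the deviation review. It needs no new data and restores the protocol's own entry criterion without altering it.

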8.3.2. Exclusion Criteria

Exclude a patient from this study if any of the following conditions are observed:

- 1. Has a serious illness or medical condition(s) including, but not limited to the following:
 - a. Other concurrently active malignancies excluding malignancies that are disease free for more than 5 years or carcinoma-in-situ deemed cured by adequate treatment.
 - b. Known brain metastasis or leptomeningeal metastasis.
 - c. Active infection (ie, body temperature ≥38°C due to infection) including active or unresolved pneumonia/pneumonitis.
 - d. Intestinal obstruction, pulmonary fibrosis, renal failure, liver failure, or cerebrovascular disorder.
 - e. Uncontrolled diabetes.
 - f. Myocardial infarction within 12 months prior to randomization, severe/unstable angina, symptomatic congestive heart failure New York Heart Association (NYHA) class III or IV
 - g. Gastrointestinal hemorrhage (Grade ≥ 3) within 2 weeks prior to randomization.
 - h. Known human immunodeficiency virus (HIV) or acquired immunodeficiency syndrome (AIDS)-related illness, or chronic or acute hepatitis B or hepatitis C.
 - Patients with autoimmune disorders or history of organ transplantation who require immunosuppressive therapy.

- j. Psychiatric disease that may increase the risk associated with study participation or study drug administration, or may interfere with the interpretation of study results.
- 2. Has had treatment with any of the following within the specified time frame prior to randomization:
 - a. Major surgery within prior 4 weeks (the surgical incision should be fully healed prior to study drug administration).
 - b. Any anticancer therapy within prior 3 weeks.
 - c. Extended field radiation within prior 4 weeks or limited field radiation within prior 2 weeks.
 - d. Any investigational drug/device received within prior 4 weeks.
- 3. Has previously received TAS-102.
- 4. Has unresolved toxicity of greater than or equal to CTCAE Grade 2 attributed to any prior therapies (excluding anemia, alopecia, skin pigmentation, and platinum-induced neurotoxicity).
- 5. Is a pregnant or lactating female.
- 6. Is inappropriate for entry into this study in the judgment of the Investigator.
- 7. Known or assumed hypersensitivity to TAS-102 or any of its ingredients.

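### SAP 9.2.2 defines major deviations in terms that differ from the protocol's eligibility criteria on adjuvant therapy (MRD4d), the washout reference date (MRD5) and, less importantly, the toxicity route (MRD4c)

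*SAP*

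**What the plan says.** **Adjuvant therapy as a prior regimen.** Protocol 8.3.1, inclusion 3, requires that the patient "Has previously received at least 2 prior regimens (at least 1 cycle per regimen) for advanced disease". Item 3d lets some adjuvant treatment count as one regimen if disease recurred during it or within 6 months of its completion: "Patients who have received postoperative adjuvant chemotherapy or chemoradiotherapy". SAP 9.2.2 turns this into MRD4, triggered by "Received fewer than 2 prior regimens (at least 1 cycle per regimen) of standard chemotherapy". Its item d reads "Patients who have received postoperative adjuvant chemotherapy and radiotherapy", and the SAP synopsis has the same wording.

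**Washout.** Protocol 8.3.2, exclusion 2b, is "Any anticancer therapy within prior 3 weeks", and the stem of exclusion 2 counts back from randomization. MRD5 is "Prior anticancer therapy within 3 weeks prior to study drug administration". Protocol 8.1 allows up to 3 calendar days between randomization and the start of study medication.

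**Toxicity route.** Protocol inclusion 3c covers "Patients who have withdrawn from their last prior regimen due to unacceptable toxicity". MRD4c covers "Patients who have withdrawn from standard treatment due to unacceptable toxicity". The SAP synopsis keeps the protocol's restriction to the last regimen.

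**Use of the definitions.** SAP 9.2.2 says that the major set measures adherence to key aspects of the protocol through pre-specified analyses whose name is redacted. Major deviations are listed and tabulated for the ITT population and for all patients, screen failures included.

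**The concern.** A deviation rule measures adherence only if it tests the criterion that the sites were told to apply. Here one rule (MRD4d) asks for more than the protocol does, so it can label an adherent patient as a major deviator. Another (MRD5) asks for less, so it can leave a true breach out of the major list. The third (MRD4c) is also looser on its face.

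At stake are the accuracy of the major-deviation tables in the study report and whatever pre-specified analyses rely on the major set. The visible text of SAP section 14, which records changes to section 9.2, gives no reason for major-deviation definitions that differ from eligibility.

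**Working it through.** The point rests on comparing definitions. The plan states no figure to reproduce, so each rule is applied to test cases.

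**1. MRD4d: regimen count.** Assume recurrence within 6 months of adjuvant therapy and all other criteria met. Regimens = advanced-disease lines + 1 if the adjuvant therapy counts, otherwise + 0. MRD4 is triggered if the count is below 2.

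| Patient | Protocol 3d | MRD4d, literal | MRD4 met? |
|---|---|---|---|
| One advanced line + postoperative chemotherapy alone | 1 + 1 = 2 | 1 + 0 = 1 | Yes |
| One advanced line + postoperative chemotherapy with radiotherapy | 1 + 1 = 2 | 1 + 1 = 2 | No |
| One advanced line + the same chemotherapy before and after surgery | 1 + 1 = 2 | 1 + 1 = 2 | No |
| Two advanced lines, any adjuvant therapy | at least 2 | at least 2 | No |

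Only the first row differs. The third row agrees because the second sentence of MRD4d matches the protocol and sets no radiotherapy condition. The first-row patient satisfies the regimen-count criterion, so RD1 (entry criteria not met, SAP 9.2.1) does not apply.

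**2. MRD5: reference date.** Let g be the days from last anticancer therapy to randomization and k the days from randomization to first dose (0 to 3, protocol 8.1). Reading within 3 weeks as under 21 days:

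- Protocol breach: g < 21.
- MRD5 flag: g + k < 21.
- Breach missed by MRD5: 21 − k ≤ g ≤ 20, which is k day-values.
- Flag without a breach: needs g ≥ 21 and g + k < 21, impossible for k ≥ 0.

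| k | Missed g, reading < 21 days | Missed g, reading ≤ 21 days |
|---|---|---|
| 0 | none | none |
| 1 | 20 | 21 |
| 2 | 19–20 | 20–21 |
| 3 | 18–20 | 19–21 |

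The error runs one way: MRD5 can miss a breach but cannot create one. A patient randomized but never dosed has no k, so MRD5 cannot be evaluated, although SAP 7.1 keeps that patient in the ITT population for which the table is made.

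**3. MRD4c: toxicity route.** The SAP phrase covers every standard treatment, the protocol phrase only the last regimen. On its own text MRD4c therefore accepts a patient who left an earlier regimen for toxicity but not the last one. However, the MRD4 stem still refers to the last prior therapy and may catch the same patient.

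**4. After alignment.** With MRD4d worded as in the protocol, the first row of the first table counts 2 and is not flagged. With MRD5 counted from randomization, the flag is g < 21, identical to the breach, and no day-value is missed at any k.

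**The case against.** **The false flag is not certain.** SAP 9.2.2 draws major deviations from among the CSR reportable ones, and the reportable category for entry failures is RD1. A patient eligible under protocol 3d has no RD1 and, on that reading, never enters the pool. This stands as a limit. But SAP 9.2 also treats anyone who meets a listed criterion as having a reportable deviation, so the text supports either reading. Under both, MRD4d names as deviant something the protocol permits.

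**Nothing disappears from the report.** RD1 captures patients who failed entry criteria, and SAP 9.4 summarizes randomized patients who did not meet them, by arm. This also stands: missed means missed from the major list only. A sponsor may choose a major set narrower than all eligibility failures, but the visible text does not say that this was the intention.

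**A reader might infer that valid patients are dropped from an analysis and violators kept.** The documents do not support that. SAP section 7 defines only the ITT, As-Treated and Tumor Response populations, and none of them uses major deviations. A per-protocol population appears only in the abbreviation list. What the redacted analyses do with the major set is unknown.

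**A reader might want a number of misclassified patients.** None can be given. The documents do not say how many patients rely on postoperative chemotherapy alone to reach two regimens, or how many were treated close to the washout limit.

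**The SAP may follow an older protocol.** SAP section 2 lists only the original protocol of 30 June 2015. That could explain the wording, but it does not remove the mismatch with the current protocol.

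**Conclusion.** The point holds as a contradiction between protocol and SAP in the definitions, and the SAP should be corrected.

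- MRD4d is the main item: read literally, it turns a protocol-eligible history into a major deviation. Only patients with postoperative-only chemotherapy who need it to reach two regimens are affected.
- MRD5 is small but definite: up to 3 day-values missed, toward under-flagging only, and undefined for patients never dosed. The day-values assume that dosing keeps to the 3-day allowance.
- MRD4c is the weakest, because the MRD4 stem partly offsets it. It is also inconsistent with the SAP's own synopsis.

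The reach is limited to the major-deviation tables and any redacted pre-specified analyses that use the major set. The primary overall survival comparison is ITT and unaffected.

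**What to change.** Before unblinding, reconcile four places in the SAP with the current protocol:

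- MRD4d and the matching bullet in the SAP synopsis: adjuvant chemotherapy or chemoradiotherapy, as in inclusion 3d.
- MRD4c: the last prior regimen, as in inclusion 3c and the SAP's own synopsis.
- MRD5: the randomization reference date of exclusion 2, which also makes the rule evaluable for patients never dosed.

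If any difference is deliberate, say so in SAP 9.2.2 and give the reason. This asks only that the deviation rule and the eligibility rule agree; it takes no position on which clinical criterion is right.

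The cost is a few phrases. No new data are needed beyond dates and treatment histories. SAP 9.2 already has deviators identified by data review before final unblinding, so the correction fits that step. Made afterwards, it would look post hoc.
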